3 OBJECTIVES AND ENDPOINTS

OBJECTIVES	ENDPOINTS	JUSTIFICATION FOR ENDPOINTS
Primary		
The primary objective of this study is to develop and validate a multi- modal digital pain reduction kit for improving physical function over time.	The primary endpoint in this study is a clinically significant change in self- reported physical function over time among individuals in the intervention arm compared to those in the active control. The outcome measure used to quantify this endpoint is the PROMIS® PF short-form, a validated self-report of physical function. The	The PROMIS® PF short- form scale is a widely validated instrument with excellent content validity, construct validity, and reliability in patients with spinal disorders and other conditions marked by

OBJECTIVES	ENDPOINTS	JUSTIFICATION FOR ENDPOINTS
	outcome measure is administered on a weekly basis via a smartphone survey to capture longitudinal change and variation among participants.	diminished mobility. The outcome measure allows us to place patients on a continuum of physical function with respect to various physical actions.
Secondary		
The secondary objective of this study is to investigate the efficacy of a multi-modal digital pain reduction kit in reducing pain interference over time, work productivity, opioid use, and satisfaction with care.	The secondary endpoints of are clinically significant changes in pain interference, work productivity, use of opioids, and satisfaction with healthcare among those in the intervention arm compared to participants in the active control. Outcome measures include pain interference (PROMIS® Pain Interference, measured weekly via smartphone surveys), work absenteeism and presenteeism (WPAI:LB, measured at baseline and exit surveys), number of 90 Morphine Milligram Equivalent opioid prescriptions (obtained via cumulative EHR records), and satisfaction with healthcare (CG- CAHPS, measured once at the conclusion of the study).	
Tertiary/Exploratory		
N/A	N/A	N/A

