4 STUDY DESIGN

4.1 OVERALL DESIGN

This RCT will enroll 174 patients with pain due to musculoskeletal injuries to test the efficacy of a multi- model digital pain reduction kit on short term pain management as an adjunct to traditional medical therapy. We will attempt to enroll a minimum of 90 patients reporting lower back pain specifically, as patients without lower back pain are less likely to use the TENS unit. Prior to adding the TENS unit to the control arm, we recruited 24 control patients. However, we will not discard their data since we intend on performing a supplementary sensitivity analysis. In addition to these 24 controls, we will randomize 75 patients to receive the study intervention (multi-modal digital pain-reduction kit with optional remote coaching support), and the other 75 patients will receive an active control. We will allocate patients using a random number generator to ensure that there is an equal distribution of participants in the control vs. experimental group. The primary outcome will be changes in self-reported physical function measured by the Patient Reported Outcome Measurement Information System (PROMIS®) Physical Function Scale. Secondary outcomes will include PROMIS® Pain Interference Scale, PROMIS® Global Health Scale, work productivity and activity impairment questionnaire (WPAI) (for patients with lower back pain specifically), patient satisfaction measured by the Pain Treatment Satisfaction Scale and SF Patient-Satisfaction Questionnaire), and use of opioids (measure in morphine milligram equivalents).

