4.2 SCIENTIFIC RATIONALE FOR STUDY DESIGN

The active control group in the randomized control trial minimizes biases related to reactivity administering standard care of care in addition to a passive measurement component. Therefore, the control group may show some effect and limit the effect size of the intervention, given that TENS units have been shown to reduce pain, at least in the short term.

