5 STUDY POPULATION

5.1 INCLUSION CRITERIA

In order to be eligible to participate in this study, an individual must meet all of the following criteria:

- 1. Provision of signed and dated informed consent form
- 2. Stated willingness to comply with all study procedures and availability for the duration of the study
- 3. Male or female, aged 18 or older
- 4. Seeking care for a musculoskeletal injury
- 5. Experiencing pain greater than 3 out of 10 on a visual analog scale
- 6. English speaking
- 7. Owns a compatible Android or iOS smartphone device (excluding tablets)

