5.5 STRATEGIES FOR RECRUITMENT AND RETENTION

Male and female participants above the age of 18 will be screened to reach target enrollment 174 patients over a period of 16 months. Participants presenting with pain due to a musculoskeletal injury will be screened and enrolled at four sites (Cedars Sinai Orthopedic Clinic, Medical Delivery Network, Cedars Sinai Pain Management Clinic, Medical College of Wisconsin). Patients will be identified and approached by their providers. The treating physicians will contact their patients during their clinic visits and assess the patient's willingness to be contacted about the research and the treating physician will document the patient's willingness to be contacted on the *CSMS Research Interest* letter. The Research Letter will be tailored to each clinical practice of the treating provider. Additionally, participating providers will distribute recruitment pamphlets to patients in clinic and/or through mail. Should the patient be interested in being contacted about the study, the study team will then approach the patient for

participation in the research either in person or over-the-phone. The patient will have the option to complete their consent forms on paper or electronically using the 21 CFR 11-compliant online platform, DocuSign. Every subject will be informed of the approximate time to complete the consent process. Consenting will be done with a research staff member either in-person or remotely via DocuSign to ensure the identity of the person signing the informed consent form is indeed the subject participating in the research study. A copy of the informed consent documents will be given to the participants for their records via their email or a physical hard copy. Participants who consent remotely will receive their study equipment through a secure FedEx package requiring a signature. Retention to the 60-day study for the intervention group will be managed using weekly reminders to complete survey protocols, as well as optional opt-in monitoring of compliance and health data via remote clinical and technical support staff. Participants will not receive monetary compensation for participating in this study.

Participants experiencing lower back pain will be oversampled to a minimum of 45 per arm in order to obtain sufficient sample size for testing the success of the TENS unit.

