For this study, we will use an over-the-counter, consumer-facing product called the Aleve Direct Relief TENS Device. This device is designed for use over the lower back for management of pain of lumbosacral origin. Treatment periods last 30 minutes and include three stages. In stage I, the device emits 5 minutes of high frequency stimulation (>50 Hz) to initiate anti-nociceptive effects through diminished processing of pain signals. In stage II, the device emits 20 minutes of low frequency stimulation (<20 Hz) to release endorphins as a second mechanism of pain reduction. The treatment period ends with stage III, in which another 5 minutes of high frequency stimulation is deployed with the aim of maintaining the initial pain relief established by phases I and II. Patients receive a handheld remote control to adjust the intensity of the electrical stimulation based on personal preference and tolerance. The device is used as needed for breakthrough pain, or as baseline prophylactic treatment.

Clinical and Technical Support

Patients in the intervention arm will not only receive the digital pain reduction kit, but also will receive remote technical and clinical support from the research team. The idea is that issuing devices is usually insufficient to achieve behavior change; supporting those device with high-touch yet scalable care is a vital component.

Rationale for "Digitalist" Model of Remote Clinical Monitoring

Integrating digital technologies into a harmonized health delivery model may improve process and outcomes of care. If used effectively, digital health monitoring may tailor care to individual patients, extend clinicians' reach outside of the hospital and clinic, improve timeliness and specificity of care, deliver proactive (not reactive) care, and better engage patients in their health.[20]

Still, there are important questions we need to answer: Who will be checking all the data? How can doctors, who are busy in the clinical trenches, be responsible for monitoring and acting upon the data streaming off wearable sensors, apps, and patient-provider portals? Who has time for this? The reality is that no doctor has enough bandwidth to check mobile health (mHealth) data on a regular basis. Clinicians are too busy for this work.[20]

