6.1.2 DOSING AND ADMINISTRATION

Participants are assigned TENS devices and VR to be used as needed. Participants are also instructed to use VR at least three times a day. The dosage for both devices will not change throughout the study. Individuals assigned to remote monitoring will be continuously monitored and any action will be physician-initiated. Participants in the control group will receive standard of care and TENS unit.

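### The trial admits any musculoskeletal injury, but the control device is described as a lower-back device; the single active-control label is weak for patients without back pain, and the primary analysis ignores back-pain status

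*Combined protocol and SAP*

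**What the plan says.** - **Who enters.** The injury criterion in section 5.1 is "Seeking care for a musculoskeletal injury", with no restriction by body site.
- **What controls receive.** Section 6.1.2: "Participants in the control group will receive standard of care and TENS unit". The synopsis (1.1) and section 6.1.1 also put a TENS unit in the intervention kit.
- **What the device is for.** Section 6.1.1: "This device is designed for use over the lower back for management of pain of lumbosacral origin". The efficacy review cited there concerns low back pain, and the section calls the wider evidence inconsistent by pain location, among other factors.
- **What the protocol expects.** Section 4.1 says "patients without lower back pain are less likely to use the TENS unit", and responds with a target: "We will attempt to enroll a minimum of 90 patients reporting lower back pain specifically". Section 5.5 sets it by arm: "Participants experiencing lower back pain will be oversampled to a minimum of 45 per arm".
- **What the endpoint compares.** Section 3 defines the primary endpoint as a change among "individuals in the intervention arm compared to those in the active control", with no reference to pain site.
- **What is analysed.** The covariate list in section 9.1 includes a chronic pain diagnosis but not lower back pain. Section 9.4.2 has no subgroup or interaction. The TENS term in section 9.4.4 is coded only as unit or no unit. Section 4.1 confines the WPAI, a secondary outcome, to patients with back pain; no other planned analysis uses back-pain status.

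**The concern.** By the protocol's own account, the comparator does not mean the same thing for every patient. A control with back pain has a device described as designed for that pain. A control with, say, an ankle injury has standard care and a device described as designed for a different site, which the protocol expects to be used less. The primary endpoint nevertheless describes one comparison with one active control.

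The quota shows that the protocol sees the issue and that back-pain status has to be recorded, but the statistical section does not carry it through. A reader of the pooled result could not tell how far the kit-versus-active-control description applies to patients without back pain, or how much the TENS unit was used in either group. The trial is unblinded and the primary outcome is self-reported (sections 6.2 and 8.1), so what the control patients actually had matters for interpretation.

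**Working it through.** **Inputs.** 75 per arm under the current protocol and 24 earlier controls without TENS (sections 1.1, 4.1, 6.2); back-pain minimum of 90 in all (4.1) and 45 per arm (5.5); ITT set of all randomised patients (9.3); 0.6 SD effect, alpha 0.05 and 25% withdrawal (9.2); SD of 10 T-points and MCID of 2 points (8.1). Two-sided testing is assumed, because 9.2 does not state sidedness.

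**The plan's own figures.** 2 × 45 = 90, so sections 4.1 and 5.5 agree. 75 + 75 + 24 = 174, so the enrolment total agrees.

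**Share without back pain.**
- Minimum just met within the 150: 75 − 45 = 30 per arm; 30/75 = 40%. Overall (150 − 90)/150 = 40%.
- Full ITT set, if only 90 in all have back pain: 174 − 90 = 84; 84/174 = 48.3%.
- Section 4.1 words the minimum as an attempt. If it is missed, the share rises; if more back-pain patients enrol, it falls.

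**What is randomised.** Among the 150:

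| Stratum | Intervention | Control |
|---|---|---|
| Back pain | standard care + TENS + VR + support | standard care + TENS |
| No back pain | standard care + TENS + VR + support | standard care + TENS |

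The assigned difference is VR plus support in both rows. Poor fit between device and injury affects both arms of the second row. The contrast is therefore not confounded; what differs between rows is how active the shared background is likely to be.

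**What section 9.4.4 can show.** Its TENS term equals 1 for all 150 current patients and 0 only for the 24 earlier controls, so it carries no information on pain site.

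**Precision by stratum**, relative to the pooled estimate at the 60/40 split:
- Back pain: √(150/90) = 1.29 times the pooled standard error.
- No back pain: √(150/60) = 1.58 times.

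**Power for 0.6 SD**, from Φ(0.6 × √(n/2) − 1.96), n per arm:

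| Set | No withdrawal | After 25% withdrawal |
|---|---|---|
| All 75 per arm | 96% | 89% (n = 56) |
| Back pain only, 45 per arm | 81% | 68–70% (n = 33–34) |

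**Interaction**, assuming SD 10, a single time point, no baseline adjustment, and 56 per arm split 33.6 and 22.4: SE = 10 × √(2/33.6 + 2/22.4) = 10 × √0.1488 = 3.9 points. The 95% half-width is 1.96 × 3.86 = 7.6 points, against the 2-point MCID. Repeated measures and baseline adjustment should reduce this, by an amount the documents do not allow one to compute.

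**The case against.** The strongest reply is that TENS is in both arms. A kit patient with an ankle injury holds the same lower-back device as the matching control, so the pooled comparison is a fair test of VR plus support. This stands.

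Section 4.2 also gives less ground for complaint than its opening suggests. It begins "The active control group in the randomized control trial minimizes biases related to reactivity", but the mechanism it then names is standard care together with passive measurement, which controls without back pain also receive. It mentions TENS as a reason why the control arm may itself improve and shrink the difference. This stands too, so loss of reactivity control should not be argued from that section.

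A reader might infer that controls without back pain have nothing usable. The documents say only that they are less likely to use the unit, give no rate, and describe a possible central action of TENS. A reader might also infer that pooling inflates the effect. If the apparent effect outside back pain were 1–3 T-points larger, the pooled estimate would move by 0.4 × 1 = 0.4 to 0.4 × 3 = 1.2 points. But the 1–3 points have no basis in the documents, and neither the size nor the direction of any shift is known.

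Finally, the protocol already oversamples back pain and collects daily TENS-use data (8.1). That limits the problem and makes it inexpensive to address. It does not supply an analysis, because section 9 never uses the information for the primary endpoint.

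**Conclusion.** The concern holds as one of interpretation and reporting; the primary comparison is not invalidated. Among the 150, the randomised contrast is valid as VR plus support on top of standard care and a supplied TENS unit. The single active-control description is not well supported for patients without back pain, and nothing planned for the primary endpoint would show how far it applies to them.

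That group is 40% of each arm if the back-pain minimum is just met within the 150, and 48% of the ITT set if only 90 of the 174 have back pain. Neither figure is a ceiling, because the minimum is only attempted. Nor does 40% mean that 40% of all randomised patients receive a weak comparator: only controls receive it, so it is 30 of the 75 current controls.

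The documents do not support moving the main conclusion to the back-pain stratum. That would reduce power after 25% withdrawal from about 89% to about 70% for 0.6 SD. The interaction would also be too imprecise (SE about 3.9 points under the stated assumptions) to serve as a test.

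**What to change.** 1. Keep the pooled ITT comparison as primary. In section 9.4.2, add lower-back-pain status at baseline as a covariate, and list it in 9.1.
2. Pre-specify a supportive model with an arm-by-back-pain interaction. Report the kit-versus-control estimate and interval in each stratum, stated to be estimation only because precision is low.
3. Tabulate TENS use from the daily questionnaires in section 8.1 by arm and back-pain status.
4. In sections 1.1, 3 and 4.2, describe the comparator as standard of care plus a supplied TENS unit, and qualify any active-control wording by the stratum results.
5. Reconcile section 3 (one active control), 5.1 (any injury), 6.1.1 (lower-back device) and 6.1.2 (unit for all controls). No clinical rule is proposed here.

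The cost is a few lines of analysis text and one table. The quota already requires back-pain status to be recorded, and TENS use is already to be collected. The drawbacks are wider intervals within strata and a slightly narrower claim about the comparator. The changes should be made before outcome data are examined by arm.

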6.1.2 DOSING AND ADMINISTRATION

Participants are assigned TENS devices and VR to be used as needed. Participants are also instructed to use VR at least three times a day. The dosage for both devices will not change throughout the study. Individuals assigned to remote monitoring will be continuously monitored and any action will be physician-initiated. Participants in the control group will receive standard of care and TENS unit.

6.2 MEASURES TO MINIMIZE BIAS: RANDOMIZATION AND BLINDING

Per the new protocol, participants will be randomized intervention or control until intervention and control groups each have 75 enrollees. In addition to these 150 participants, the group of 24 controls that were originally recruited without the TENS unit will remain accounted for in the supplementary analysis. There will be no blinding, as participants in the control group will be aware that they are missing components of the intervention as detailed in the consent form.

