9.4.4 ACCOMODATING ADDITION OF TENS UNIT TO THE CONTROL ARM

An ITT analysis "Includes all randomized patients in the groups to which they were randomly assigned, regardless of their adherence with the entry criteria, regardless of the treatment they actually received, and regardless of subsequent withdrawal from treatment or deviation from the protocol."^{ref} Accordingly, we will follow the original analysis plan described above with regard to analyzing results by study-arm. In addition to the ITT analysis, however, we will conduct a sensitivity analysis by repeating the statistical procedures in a per-protocol fashion wherein the members of the control arm who did not receive a TENS unit will be dropped from the sample. Directions, magnitudes, and significance of treatment effects will be presented for both analyses.

Furthermore, because the TENS unit will appear in both study arms - and unevenly in the control arm – we recognize that an ITT analysis strictly *by* study-arm risks misidentifying the effect of treatment, while a per-protocol analysis risks introduction of bias. Therefore, we will conduct an additional linear mixed model regression analysis using a term for the TENS that captures the effect of the TENS separately from the effects of study-arm assignment. The model used to fit these data is as follows:

 $\hat{y}_{it} = \beta_0 + \beta_1 time_{it} + \beta_2 study_arm_{it} + \beta_3 TENS_{it} + e_{it}$

where time represents change in time from baseline, study_arm indicates status as a control or experimental participant (0= control and 1=experimental), *i* is the individual participant, and TENS indicates TENS unit usage (0= no TENS unit and 1=TENS unit). We can therefore write a regression equation describing each type of patient differentiated by the addition of the TENS unit to control conditions:

Treatment: $\hat{y}_{it} = \beta_0 + \beta_1 time_{it} + \beta_2 study_arm_{it} + \beta_3 TENS_{it} + e_{it}$

Control w/o TENS: $\hat{y}_{it} = \beta_0 + \beta_1 time_{it} + e_{it}$

Control w/ TENS:

 $\hat{y}_{it} = \beta_0 + \beta_1 time_{it} + \beta_3 TENS_{it} + e_{it}$

In this manner we isolate the term of interest (study_arm). Given we are only adding one term but 20 subjects, we are comfortable relying on the original power calculation.

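### The primary dataset (150 or 174) is not settled for the 24 controls without TENS, and the by-arm ITT that includes them does not estimate kit versus TENS control

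*Combined protocol and SAP*

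**What the plan says.** Section 4.1 explains that 24 control patients were recruited before TENS was added to the control arm, and that "we will not discard their data since we intend on performing a supplementary sensitivity analysis". It adds 75 kit and 75 active-control patients to these. Section 6.2 repeats the structure: randomisation continues to 75 per group, and beyond those 150, "the group of 24 controls that were originally recruited without the TENS unit will remain accounted for in the supplementary analysis".

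Section 9.3 puts every randomised participant in the dataset. Section 9.4.4 states that "we will follow the original analysis plan described above with regard to analyzing results by study-arm", under ITT. Its sensitivity analysis, labelled per-protocol, is the one in which "the members of the control arm who did not receive a TENS unit will be dropped from the sample". It accepts that a strict by-arm ITT "risks misidentifying the effect of treatment, while a per-protocol analysis risks introduction of bias". It therefore adds a mixed model with terms for time, study arm and TENS, and says of it: "In this manner we isolate the term of interest", meaning study arm. That model is described as additional.

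Section 3 defines the primary endpoint as kit versus active control. The synopsis and section 6.1.2 say that controls receive a TENS unit. The synopsis counts 75 kit, 75 control with TENS and 24 control without TENS, 174 in all. Section 9.4.4 puts the added subjects at 20.

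**The concern.** The two pairs of sections reverse which analysis is supplementary. In 4.1 and 6.2 the 24 come in for the supplementary analysis; in 9.4.4 they are taken out for it. A reader cannot tell whether the headline result rests on 150 or 174 patients.

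The choice also changes the quantity estimated. A control arm in which about a quarter had no TENS is not the active control of the synopsis. If TENS improves physical function, the pooled contrast credits the kit with part of the benefit of a device that both arms now receive. The trial is unblinded and no analysis is named as primary for kit versus TENS control, so the choice should be fixed before the results are seen.

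**Working it through.** **Inputs.** Group sizes 75, 75 and 24 (synopsis); 20 added subjects (9.4.4); MCID 0.2 SD (8.1); design effect 0.6 SD, 80% power, level 0.05, 25% withdrawal (9.2). Assumed because the documents do not give them: two-sided testing, the TENS effect on PROMIS PF, any shift between periods, and m, the number of the 75 kit patients randomised before TENS was added.

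**1. The plan's own sample size.** n per arm = 2(1.960 + 0.842)²/0.6² = 43.6, so 44 evaluable (45 by exact t). Dividing by 0.75 gives 59 to 60 randomised per arm, 118 to 120 in total. The stated 120 per arm and 245 in total do not reproduce. That is a separate matter; here it matters only that 75 per arm exceeds 59 to 60.

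**2. What the by-arm ITT estimates.** Write K, T and N for the mean outcomes of kit, TENS control and control without TENS. The pooled control mean is (75T + 24N)/99, so

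ITT = K − (75T + 24N)/99 = (K − T) + (24/99)(T − N) = kit-versus-TENS effect + 0.242 × TENS effect.

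With 20 instead of 24, the weight is 20/95 = 0.211.

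| Assumed TENS effect (SD) | Added to the contrast, 24 | Added, 20 | Share of MCID, 24 |
|---|---|---|---|
| 0 | 0 | 0 | 0% |
| 0.1 | 0.024 | 0.021 | 12% |
| 0.2 | 0.048 | 0.042 | 24% |
| 0.3 | 0.073 | 0.063 | 36% |
| 0.4 | 0.097 | 0.084 | 48% |

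If the kit adds nothing over TENS, the two-sided rejection rate at 75 versus 99 is 6.2% for a TENS effect of 0.2 SD and 9.7% for 0.4 SD, instead of 5%. These are identities in group means; a mixed model with missing weeks will weight patients slightly differently.

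**3. What the TENS-term model estimates.** There are three groups and, apart from time, three parameters. The study-arm coefficient is therefore K − T, the same contrast as dropping the 24. Its standard error is √(2/75) = 0.163 SD, against √(1/75 + 1/99) = 0.153 SD for the pooled ITT.

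**4. Power for that contrast.** At 0.6 SD with 25% loss (56 per arm): 0.6/√(2/56) = 3.175, and Φ(3.175 − 1.960) = 0.888 (0.882 by exact t). The pooled ITT at 56 versus 74 gives 0.923.

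**5. Period.** TENS = 0 occurs only in controls enrolled before the change. Let s be the late-minus-early shift in the analysed outcome, with no treatment effects. The kit mean is (75 − m)s/75, the TENS-control mean is s, and the early-control mean is 0. Then:

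- study-arm coefficient (and drop-24 contrast): −(m/75)s;
- TENS coefficient: s, so it carries the whole shift;
- by-arm ITT: (24/99 − m/75)s.

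For an assumed s of 0.3 SD, the study-arm bias is 0 at m = 0 and −0.096 SD at m = 24; the ITT carries +0.073 and −0.023 SD. A before/after period term cannot be fitted at m = 0, because it duplicates the TENS term. At m > 0 it makes the arm coefficient late kit minus late TENS control, with standard error 1.11 times larger at m = 24.

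**The case against.** The strongest reply is that 9.4.4 already handles the matter. It discloses the mixture, promises direction, magnitude and significance for both the ITT and the drop-24 analysis, and adds a model aimed at the study-arm term. The statistical sections agree with each other, and the supplementary analysis in 6.2 could be the TENS-term model. Much of this stands: the right contrast is planned, and what is missing is its status and agreement among the sections.

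It can also be said that active control is looser than the synopsis suggests. Section 4.2 describes it first as standard care with passive measurement, and the population row counts the 24 as controls. That is fair, but the synopsis and 6.1.2 say plainly that controls receive TENS.

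Three stronger readings are tempting and not supported:

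- **That 4.1 and 6.2 exclude the 24 from the main analysis.** They assign them to a supplementary one without saying that they are in no other.
- **That the planned study-arm coefficient is biased by drift.** This needs m > 0 and a real shift. Neither is given, and 4.1 reads most naturally as m = 0. It remains open because 174 = 75 + 75 + 24 leaves room for early kit patients only within the 75, and 4.1 intends that "there is an equal distribution of participants in the control vs. experimental group".
- **That the primary set must be limited to patients randomised concurrently after the change.** If m > 0 this drops randomised kit patients and may cost power. How much depends on whether the 75s are counted after the replacement of withdrawn participants in 7.2: at m = 24 with concurrent controls only, about 74% if not and about 85% if so.

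**Conclusion.** The point holds. The documents do not settle whether the primary dataset is 150 or 174 (before any replacement of withdrawals), and the by-arm ITT with the 24 included targets a mixture rather than the stated comparison. The weight on the TENS effect is 0.242, or 0.211 if 20 is the correct count. The resulting 0.02 to 0.10 SD rests on an assumed TENS effect of 0.1 to 0.4 SD. The upper values are illustrative, since 4.1 itself expects that "patients without lower back pain are less likely to use the TENS unit". With no TENS effect on physical function and no drift, the distortion is zero. The period issue is a question for the sponsor, not a demonstrated bias. This should be fixed because it decides what the primary result means, although the needed analysis is already in the plan.

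**What to change.** - Make 4.1, 6.2, 9.3 and 9.4.4 agree: the primary contrast is kit versus TENS control, estimated by the study-arm coefficient of the TENS-term model. Report the pooled by-arm analysis of all randomised participants as supplementary, so no data are discarded.
- Reconcile 20 and 24.
- State m. If m = 0, do not interpret the TENS coefficient as a TENS effect, because it is aliased with period. If m > 0, report the same model with a before/after period term as a sensitivity analysis. Encounter month is only a potential covariate in 9.1 and is not in the 9.4.4 equation.
- Call the drop-24 analysis a restriction to the amended control. The label per-protocol does not fit, since these patients received what they were assigned.

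The cost is wording in four sections and one reported count. The standard error rises from 0.153 to 0.163 SD. Power at 0.6 SD with 25% loss falls from about 92% to about 88%, still above the stated 80%.
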